8.1 Screening

All procedures must be conducted after getting ICF, and participant numbers are assigned in the order of consent. Screening is performed to assess inclusion/exclusion criteria (Refer to the value of Section 8.2).

8.1.1 Information to be collected on screening failures

Participants who sign an ICF and subsequently found to be ineligible prior to randomization will be considered a screen failure. The reason for screen failure should be recorded on the electronic case report form (eCRF). The demographic information, informed consent, and inclusion/exclusion pages must also be completed for screen failure participants.

Participants who are randomized and fail to start study (e.g., participants randomized in error) will be considered an early terminator. The reason for early termination should be recorded on the eCRF.

8.2 Participant demographics/other baseline characteristics

The following patient demographic and other baseline characteristics data will be collected on all participants.

8.2.1 Demographic characteristics

The following information will be collected/documentated at screening for each patient:

- Year of birth
- Age
- Sex
- Height (cm)
- Weight (kg)
- BMI
- Alcohol consumption status (current drinker, past-drinker or non-drinker)
- Smoking status (current smoker, ex-smoker or never smoked)

8.2.2 Medical history and medication

8.2.2.1 Medical history

- Heart diseases (presence or absence/start date/end date/ongoing or not)
- Stroke (presence or absence/start date/end date/ongoing or not)
- Diabetes (presence or absence/start date/end date/ongoing or not)
- Hyperlipidemia (presence or absence/start date/end date/ongoing or not)
- Hypertension (presence or absence/start date/end date/ongoing or not)

- Fatty liver (presence or absence/start date/end date/ongoing or not)
- Other diseases (presence or absence/disease name/start date/end date/ongoing or not)

8.2.2.2 PsO related medical history

- Date of diagnosis for PsO
- Family history of PsO
- Family history of PsA
- PASI score
- Hard-to-treat area involvement (presence or absence of scalp, palmoplantar and nails)
- Musculoskeletal symptoms (presence or absence/site)

8.2.2.3 Medications

- Presence or absence of medications
- Drug name
- Daily dose
- Route of administration
- Administration period (start date/end date/ongoing or not)
- Purpose of administration (PsO related/others)

8.2.2.4 PsO related treatment other than medications

- Presence or absence of PsO related treatment
- Treatment name
- Treatment period (start date/end date/ongoing or not)

8.3 EARP

The EARP is a questionnaire composed of ten questions regarding symptoms of joint disease, developed for the early diagnosis of PsO. This questionnaire consists of simple questions, and it has 0-10 range (Tinazzi I, et al. 2012).

In this study, the EARP screening is only conducted on the EARP group, and when the EARP score ≥ 3 , it can be judged that the patients is potential PsA. The Korean EARP questionnaire is included in Appendix 1. EARP questionnaire.

- EARP score

8.4 Physical examinations

8.4.1 NAPSI

The nails will be visually inspected, and if an abnormality is observed, a photograph will be obtained and will be evaluated by investigator using NAPSI.

NAPSI is a numeric, reproducible, objective, simple tool for evaluation of nail PsO. This scale is used to evaluate the severity of nail bed PsO and nail matrix PsO by area of involvement in the nail unit. The nail is divided with imaginary horizontal and longitudinal lines into quadrants. Each nail is given a score for nail bed PsO (0-4) and nail matrix PsO (0-4) depending on the presence of any of the features of nail PsO in that quadrant (Rich P, et al. 2003). A total score per nail is 0-8, and the range of the total scores from all nails is 0-160 (toenails are included).

In this study, NAPSI is measured for all participants.

- Score of left hand
- Score of right hand
- Score of left foot
- Score of right foot
- Total score

Figure 8-1 NAPSI score

Nail Psoriasis Severity Index (NAPSI)

The target nail is graded from nail matrix psoriasis and nail bed psoriasis. The sum of these two scores is the total score for that nail.

Score for matrix psoriasis	_____
0 = none	
1 = present in 1/4 nail	
2 = present in 2/4 nail	
3 = present in 3/4 nail	
4 = present in 4/4 nail	

Nail Matrix Psoriasis consists of any of the following: pitting, leukonychia, red spots in the lunula, and nail plate crumbling.

Score for nail bed psoriasis	_____
0=none	
1 = present in 1/4 nail	
2 = present in 2/4 nail	
3 = present in 3/4 nail	
4 = present in 4/4 nail	

Nail Bed Psoriasis is the presence or absence of any of the following: onycholysis, splinter hemorrhages, oil drop (salmon patch) discolouration, and nail bed hyperkeratosis.

[figure not shown]
Total for nail _____ (0-8)

8.4.2 SJC66/TJC68

The SJC66/TJC68 is the first instrument fully endorsed within the PsA core outcome measurement set. The 66 swollen and 68 tender joints are assessed (the hips are not assessed for swelling). The joint count is scored as a sum of the tender joints and a sum of the swollen joints (Duarte-García A, et al. 2019).

In this study, SJC66/TJC68 gets measured for all participants.

- SJC66: number of swollen joints
- TJC68: number of tender joints

Figure 8-2 SJC66/TJC68 score

8.5 Efficacy

All efficacy assessments should be recorded in the eCRF. The methods of evaluation and the primary and secondary parameter to be assessed are listed in this section.

8.5.1 Primary endpoint

The primary endpoint of this study is detection rate of PsA. The assessments are measured by the CASPAR including clinical assessment, radiography and blood test. In addition, some values which are included the CASPAR are replaced by the values in Section 8.2.

8.5.1.1 CASPAR

In this study, the CASPAR will be measured for all participants after the EARP questionnaire evaluation and the investigator's judgement are completed in each group. The details of the CASPAR scoring are in the Table 8-2 (Cantini F, et al. 2010).

Table 8-2 CASPAR score

To meet the CASPAR, a patient must have an inflammatory articular disease (inflammatory joint (peripheral) disease, enthesitis, or inflammatory axial disease) with ≥ 3 points from the above criteria.

Criteria	Point
Current PsO	2
Personal history of PsO	1

To meet the CASPAR, a patient must have an inflammatory articular disease (inflammatory joint (peripheral) disease, enthesitis, or inflammatory axial disease) with ≥ 3 points from the above criteria.

Criteria	Point
Family history of PsO	1
Typical PsO nail dystrophy (onycholysis, pitting, hyperkeratosis)	1
Current dactylitis or history of dactylitis	1
Negative rheumatoid factor	1
Hand and foot plain radiography (evidence of juxta-articular new bone formation in hand (including wrist) and feet (including ankle))	1

The items for the CASPAR measurement are as follows.

- Clinical assessment

Inflammatory joint disease (presence or absence of Inflammatory joint (peripheral) disease, enthesitis and inflammatory axial disease), date of diagnosis for PsO[#], family history of PsO[#], presence or absence of typical psoriatic nail dystrophy (onycholysis, pitting, hyperkeratosis), presence or absence of dactylitis, history of dactylitis
- Blood test

Rheumatoid factor
- Radiography

Hand and foot plain X-ray (evidence of juxta-articular new bone formation in hand (including wrist) and feet (including ankle))

Note) #: These values which are included the CASPAR are replaced by the values in Section 8.2.2.2.

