The Classification Criteria for Psoriatic Arthritis (CASPAR) were developed by an international group of rheumatologists in 2006 to help standardize the diagnosis of PsA. These classification criteria consist of two groupings: the stem (or required criteria) consist of inflammatory joint (peripheral) disease, enthesitis, and inflammatory axial disease and criteria is associated with a numerical value (Mease PJ, et al. 2014) (Taylor W, et al. 2006). To fulfill the CASPAR criteria, a patient must present with at least one of the stem components and get 3 points or higher from the criteria. The criteria include clinical assessment (current PsO or a personal/family history of PsO, psoriatic nail dystrophy, and current dactylitis or history of dactylitis), radiography (juxta-articular new-bone formation), and blood test (negative test result for the presence of rheumatoid factor). Since skin lesions classically precede joint symptoms, dermatologists are in ideal position to play a key role in identifying patients at risk for PsA before irreversible joint damage occurs (Busse K, et al. 2010) (Belinchón I, et al. 2020). However, the CASPAR criteria are not usually performed routinely in dermatology clinics, so the diagnosis of PsA in PsO patients can sometimes be overlooked. Therefore, it seems as though there is a need for a simple tool that could assist early and active diagnosis of PsA in dermatology.

There are several screening tools for PsA; the Psoriasis Epidemiology Screening Tool (PEST), the Psoriatic Arthritis Screening and Evaluation (PASE) and the Early Arthritis for Psoriatic Patients (EARP) questionnaire. These follow a similar questionnaire structure and have all been validated in patients with PsO. Among these, the EARP questionnaire is a simple, user-friendly and easy to administer screening tool. And it focuses on early diagnosis of PsA and has a higher

sensitivity than the PASE and PEST questionnaires (Iragorri N, et al. 2018). Thus, the EARP questionnaire could assist dermatologists in screening of the potential PsA patients and make early diagnosis of PsA. Also, there are studies which have shown that the detection rate of PsA can be improved via active screening of PsO patients (Mahmood F, et al. 2017).

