5.1 Inclusion criteria

Participants eligible for inclusion in this study must meet **all** of the following criteria:

1. Patient who is \geq 19 years of age at the time of study enrollment
2. Patient who had an established diagnosis of PsO based upon clinical evidence and documented medical history
3. Patient who is moderate to severe PsO (PASI score \geq 10)
4. Patient who is willing and able to comply with study procedures
5. Patient who is able to provide the informed consent form (ICF)

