	Smoking status	X			
Pregnancy tests ²⁾	X				
Inclusion/exclusion criteria	X				
Medical history and medication ³⁾	Medical history	X			
	PsO related medical history	X			
	Medications	X			
	PsO related treatment other than medications	X			
Randomization			X		
Intervention	EARP screening (EAPR group)			X	
	Investigator's judgement (Routine practice group)			X	
Physical examination	NAPSI				X
	SJC66				X
	TJC68				X

Period	Screening	Randomization	Intervention	Physical examination	Evaluation
Visit Name	Visit 1				
Day/Week/Month	Day 1				
CASPAR ⁴⁾	Clinical assessment				X
	Blood test				X
	Radiography				X

PsO; Psoriasis; EARp: Early arthritis for psoriatic patients; NAPSI: Nail psoriasis severity index; SJC: Swollen joint count; TJC: Tender joint count; CASPAR: Classification criteria for psoriatic arthritis; PsA: Psoriatic arthritis

- 1) All procedures must be conducted after getting ICF, and participant numbers are assigned in the order of consent.
- 2) For all female patients of child bearing potential only, a urine-HCG test will be performed.

3) Medical history and medication

- Medical history: Heart diseases, stroke, diabetes, hyperlipidemia, hypertension, fatty liver and other diseases
- PsO related medical history: Date of diagnosis for PsO, family history of PsO, family history of PsA, PASI score, hard-to-treat area involvement (scalp, palmoplantar and nails), musculoskeletal symptoms
- Medications
- PsO related treatment other than medications

4) CASPAR: Based on the CASPAR, participants are diagnosed with or without PsA.

- Clinical assessment: Inflammatory articular disease (inflammatory joint (peripheral) disease, enthesitis, and inflammatory axial disease), date of diagnosis for PsO#, family history of PsO#, presence or absence of typical psoriatic nail dystrophy (onycholysis, pitting, hyperkeratosis), presence or absence of dactylitis, history of dactylitis (recorded by rheumatologist)
- Blood test: Rheumatoid factor
- Radiography: Hand and foot plain X-ray (evidence of juxta-articular new bone formation in hand (including wrist) and feet (including ankle))

Note) #: These values which are included the CASPAR are replaced by the values in Section 8.2.2.2.

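### Table 8-2 lists current psoriasis, personal history and family history as separate CASPAR rows with no rule that only one counts; added as printed, every participant already has 3 points and the cut-off of 3 does no work

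*Protocol*

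**What the plan says.** Protocol Section 8.5.1.1 makes CASPAR the reference standard. Two conditions must hold: "a patient must have an inflammatory articular disease" (peripheral joint disease, enthesitis or axial disease), and this must come "with ≥ 3 points from the above criteria".

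Table 8-2 then lists seven scored rows:

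- current psoriasis, 2 points
- "Personal history of PsO", 1 point
- "Family history of PsO", 1 point
- nail dystrophy, 1 point
- dactylitis, current or past, 1 point
- "Negative rheumatoid factor", 1 point
- juxta-articular new bone on hand or foot X-ray, 1 point

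No condition links the three psoriasis rows. Section 1.1 describes the same element as "current PsO or a personal/family history of PsO", which reads as one item with alternatives.

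The notes under Table 8-1 and in Section 8.5.1.1 mark date of psoriasis diagnosis and family history of psoriasis as CASPAR inputs: "These values which are included the CASPAR are replaced by the values in Section 8.2.2.2". No separate personal-history field is listed.

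SAP 1.2 and 2.4.1 repeat the cut-off of 3 without saying how the score is built. SAP Section 4 reports no change from the protocol.

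**The concern.** Points printed in separate rows against a points threshold are naturally added. Every participant meets inclusion criterion 3 (PASI of at least 10), so has current psoriasis. Every participant also meets inclusion criterion 2, an "established diagnosis of PsO based upon clinical evidence and documented medical history". A site or programmer who follows the table literally can award both rows to everyone and reach the cut-off before any joint-specific item is assessed.

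CASPAR status decides who is a true positive, so it determines the primary endpoint and also sensitivity, specificity, PPV and NPV. Sections 1.1 and 8.5.1.1 support different reference standards. Sites that treat the psoriasis rows as alternatives would classify some patients differently from sites that add them. The patients affected are those with RF-positive inflammatory arthritis and no other psoriatic feature, whom the RF item is there to separate. Exclusion criterion 5 removes known rheumatoid arthritis, but undiagnosed cases can still be enrolled.

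**Working it through.** **1. The plan's own figure.** The sample size reproduces. (1.96 + 0.842)² × (0.09 × 0.91 + 0.197 × 0.803) / 0.107² = 164.64, taken as 165 per group; 165 / 0.90 = 183.3, taken as 184; total 368. The scoring question does not alter this calculation.

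**2. Points at entry.**

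- Rows added: 2 (criterion 3) + 1 (criterion 2) = 3, equal to the cut-off. Range 3 to 8, the maximum being 2 + 1 + 1 + 1 + 1 + 1 + 1.
- Rows as alternatives: 2. Range 2 to 6, the maximum being 2 + 1 + 1 + 1 + 1.

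**3. Which item patterns reach 3.** Five yes/no items remain (family history, nails, dactylitis, negative RF, new bone), giving 2⁵ = 32 patterns. These are patterns, not patient frequencies.

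| Reading of the psoriasis rows | Starting points | Patterns reaching 3 | Patterns that fail |
|---|---|---|---|
| All three added | 3, plus family history | 32 of 32 | none |
| Current or personal counted once, family history added | 2, plus family history | 31 of 32 | RF-positive, no other item, no family history |
| One item, scored once | 2 | 30 of 32 | RF-positive, no other item, with or without family history |

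**4. Share of participants who change class between the first and third readings.** With inflammatory disease required, this share among those who have it is

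P(RF-positive) × P(no nail dystrophy) × P(no dactylitis) × P(no new bone).

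The documents give none of these. I assume independence, RF-positive 5–15%, nail dystrophy 30–70%, dactylitis 5–30% and new bone 5–30%.

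- Low: 0.05 × 0.30 × 0.70 × 0.70 = 0.7%
- Middle: 0.10 × 0.50 × 0.85 × 0.85 = 3.6%
- High: 0.15 × 0.70 × 0.95 × 0.95 = 9.5%

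A cruder version, with RF-positive 5–15% and none of the other features in 30–60%, gives 0.05 × 0.30 = 1.5% to 0.15 × 0.60 = 9%. Both come to about 1–9%. The ceiling is the RF-positive share itself.

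**5. Effect on the planned comparison.** Suppose the planned 9% and 19.7% were obtained with the rows added, and the same share is lost from both arms.

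- Planned true positives at 165 per group: EARP 0.197 × 165 = 32.5; Routine practice 0.09 × 165 = 14.9.
- Lost in the EARP group: 32.5 × 0.007 = 0.2 to 32.5 × 0.095 = 3.1.
- Lost in the Routine practice group: 14.9 × 0.007 = 0.1 to 14.9 × 0.095 = 1.4.
- Difference between arms: 10.7 points falls to 10.7 × 0.993 = 10.6, or to 10.7 × 0.905 = 9.7.
- Power at 165 per group, pooled-variance test: 79.4% falls to 79.1% (0.7% lost), 77.7% (3.6%) or 74.7% (9.5%).

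**The case against.** The strongest reply is that addition is never stated. Table 8-2 is silent, and Section 1.1 joins the items with the word or. Separate rows would be needed even for alternatives, because current and past psoriasis carry different points. Dactylitis fits in one row because both of its forms carry 1 point. Personal history beside current psoriasis can be read as past psoriasis only. Listing date of diagnosis and family history as inputs shows that they are collected, not that they are summed. The table also breaks across a page at these rows, so the formatted document should be checked for a merged cell or footnote. All of this stands: the defect is an unresolved conflict between Section 1.1 and Table 8-2, not a declared additive rule. It does not remove the defect. The table is the operative scoring instruction, it carries no exclusivity rule in the text, and the SAP supplies none.

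A second reply is that the cut-off is weak in this population under either reading, since with the rows as alternatives a negative RF alone brings a participant to 3. That also stands, and it limits the size of the problem.

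A reader might infer that the score tilts the comparison towards EARP, because RF-positive patients with joint symptoms would score high on the questionnaire. The documents do not show this. The same scoring applies in both randomised arms, and Section 6.1.2 lets Routine practice investigators ask about current or past joint pain, so they may suspect the same patients.

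**Conclusion.** Wrong as written; moderate severity. Table 8-2 and Section 1.1 do not give the same rule. Followed literally, the table makes its own threshold inert, so that nails, dactylitis, RF and X-ray cannot affect the reference standard. Current psoriasis plus personal history is enough for this; family history is not needed, and not every participant has one.

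A reader might go further and infer that CASPAR no longer separates PsA from non-PsA at all. Nobody would then fall below 3, specificity would be 0/0, PPV 100%, NPV 0%, and the detection rate would equal the screen-positive rate. That follows only if the inflammatory disease requirement is dropped as well. The true-positive definitions in Protocol Sections 2 and 12.4.1 and SAP 1.2 and 2.4.1 do mention only the score. However, Protocol Sections 3 and 8.5.1.1 require inflammatory articular disease for a PsA diagnosis, and with that applied the reference standard still discriminates.

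The practical gap is then about 1–9% of participants with inflammatory disease, roughly 0 to 3 EARP true positives. Power falls from 79.4% to between 79.1% and 74.7% if the loss is equal in both arms. These sizes rest on assumed feature frequencies and on independence. The score arithmetic does not: it needs only the table and the inclusion criteria.

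**What to change.** Reconcile Table 8-2 with Section 1.1 by making psoriasis one item scored once: current psoriasis 2; otherwise personal or family history 1. Date of diagnosis and family history stay as descriptive characteristics, but add nothing for a participant with current psoriasis.

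In SAP 2.4.1, derive CASPAR status from the eCRF components rather than from a total entered by the site. PsA is present if inflammatory articular disease is present AND

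2 + nail dystrophy + dactylitis + negative RF + new bone formation ≥ 3 (range 2 to 6).

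The constant 2 is the psoriasis item for anyone who meets inclusion criterion 3; for a participant randomised in error without current psoriasis, use the item itself. Use this status in all four cells of the 2 × 2 tables, so that the inflammatory disease requirement sits inside the endpoint definition.

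Cost: one table correction by protocol amendment and one derivation in the SAP, made before database lock and recorded in SAP Section 4. The components are already scheduled in Table 8-1, so no new visits, tests or participants are needed. The downside is that counted PsA may fall slightly, with the small loss of power shown above.

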8.5.2 Secondary endpoint

The secondary endpoints of this study are as follows.

- Sensitivity, specificity, PPV and NPV
- Description of demographic characteristics, medications and PsO related characteristics

Sensitivity, specificity, PPV and NPV will use CASPAR to determine PsA diagnosis, and be compared between EARP questionnaire (EARP group) and the investigator's judgement (Routine practice group) (Section 8.5.1.1).

Description of demographic characteristics, medications and PsO related characteristics will be compared between PsA and non-PsA patients. Details of the variables are in Section 8.5.2.1 to 8.5.2.3 and the assessment will be measured by the values in Section 8.2 and 8.4.

8.5.2.1 Demographic characteristics

- Age
- Sex
- BMI

- Alcohol consumption status
- Smoking status

8.5.2.2 Medications

- Drug name

8.5.2.3 PsO related characteristics

PsO related medical history

- Duration of PsO
- Family history of PsO
- Family history of PsA
- PASI score
- Presence or absence of hard-to-treat area involvement (scalp, palmoplantar, nails)
- Presence or absence of musculoskeletal symptoms
- Presence or absence of PsO related treatment other than medications

Co-morbidities

- Presence or absence of co-morbidities (heart diseases, stroke, diabetes, hyperlipidemia, hypertension, fatty liver)

NAPSI

- Total Score

SJC66/TJC68

- SJC66: number of swollen joints
- TJC68: number of tender joints

8.6 Safety

Safety assessment is not applicable as no drug is involved.

8.7 Additional assessments

No additional tests will be performed on participants entered into this study.

9 Discontinuation and completion

9.1 Discontinuation from study treatment and from study

Not applicable

9.2 Withdrawal of informed consent/Opposition to use data/biological samples

Withdrawal of consent/opposition to use data occurs when a participant:

- Explicitly requests to stop the use of their data (opposition to use participant's data)
- and
- No longer wishes to participate in this study

This request should be in writing (depending on local regulations) and recorded in the source documentation.

In this situation, the investigator should make a reasonable effort to understand the primary reason for the participant's decision to withdraw their consent/opposition to use data and record this information.

Where consent to the use of Personal and Coded Data is not required in a certain country's legal framework, the participant therefore cannot withdraw consent. However, they still retain the right to object to the further collection or use of their Personal Data.

Study must be discontinued and no further assessments conducted.

Novartis will continue to retain and use all research results (data) that have already been collected for the study evaluation. No new Personal Data will be collected following withdrawal of consent/opposition.

